## **H. Human Subjects Protections and Data Sharing**

### **Describe any potential direct benefits to subjects. If there are no direct benefits, state this.**

The health benefits of quitting smoking are considerable and the current study may increase the likelihood that study participants will successfully quit by proactively offering a second round of evidence-based treatment to WTQL callers who did not achieve lasting abstinence following a prior round of treatment. All treatments used in this study have been demonstrated to be effective compared to unaided quitting in clinical practice guidelines and/or multiple research studies.

### **Describe the potential benefits of this research to society.**

This experiment will generate knowledge regarding the efficacy, cost-effectiveness, and reach of interventions that can be delivered remotely and inexpensively (with few physical or financial barriers) to a high-priority population, low-income smokers who have benefited less from existing interventions and delivery methods than have higher-income smokers. The results of this study have the potential to identify highly efficient and cost-effective means of enhancing abstinence rates in this high priority population, and thereby to reduce socioeconomic disparities in the burden of tobacco use. These results also have the potential to inform the design and delivery of public benefit programs (e.g., state quit lines) serving the target population of low-income smokers. This may reduce the substantial individual and societal costs of tobacco use and related productivity losses, disease, and death.

### **Describe any potential psychosocial risks to subjects, such as psychological stress or confidentiality risks (including risk to reputation, economic risks, and legal risks).**

Risks associated with this research are judged to be minimal, consistent with the minimal risks associated with use of nationally available smoking cessation quit line and text messaging services.

The processes of collecting treatment engagement, self-report, and biochemical (breath and urine) data carry minimal risks, and sensitive questions (e.g., regarding illegal behaviors) will not be asked. Despite this and the safeguards to protect participant information we will apply, breach of confidentiality is a risk that cannot be eliminated completely. There is a remote possibility that a subject's identity will become known to unauthorized persons.

In addition, NRT may cause side effects. NRT risks are well-documented, given their wide-scale use and over-the-counter availability (in both of the forms to be used here: patch and lozenge). Use of the nicotine patch may lead to dizziness, nausea, vomiting, rapid heartbeat, weakness, skin irritation at the site of application, sleep disturbance, rapid heartbeat, headache, and muscle

or joint aches and stiffness. According to the package insert, the most likely side effects associated with the nicotine lozenge are heartburn, hiccup, nausea, upper respiratory tract infections, coughing and sore throat. These NRT side effects are typically mild to moderate, even when individuals smoke while using nicotine replacement and the symptoms typically subside when NRT use is reduced or discontinued. It is important to note that quit lines currently screen clients for medication eligibility, dispense NRT via mail in many states, including Wisconsin, and that some currently dispense combination nicotine replacement (patch with gum, or patch with lozenge). As such, the proposed study procedures should not pose additional risks of medication side effects above and beyond current quit line practices.

An additional risk is the experience of aversive nicotine withdrawal symptoms upon cessation, such as sleep disturbance, hunger, craving, difficulty concentrating, and negative mood. These symptoms are temporary and pose minimal health risk.

Providing breath and urine samples for biochemical verification of abstinence carries minimal risks, as these procedures are non-invasive. Risks from study participation are deemed to be much lower than the known health risks of continued smoking.

**Describe how ALL the risks of the study will be minimized.**

To protect against breach of confidentiality or violations of privacy, we will ensure that data are stored on secure, encrypted servers at all participating sites, and that transfer of data between sites is conducted via HIPAA-compliant means. A unique study ID will be used to store all data on individual participants and information linking that study ID to participant identifying information will be maintained by the data manager. Data being used for analysis will be identified with the study ID only. Participant contact information will only be available to study staff having direct contact with participants. Data will be stripped of direct identifiers (limited datasets) or completely de-identified prior to sharing with others outside the IRB-approved research team.

To protect against adverse reactions to over-the-counter nicotine medication, the WTQL will screen participants for eligibility using their standard, physician-reviewed protocol over the phone and participants will receive simple, clear instructions in their proper use in the mailing sent post-enrollment. These forms will advise participants of common side effects and will describe ways to prevent or address these (i.e., putting a new patch on a different part of the body each day, taking the patch off at night if sleep disturbance is too bothersome). These medication instruction forms and all written study materials will be written at no higher than a sixth-grade reading level. In addition, people who report recent cardiac-related surgeries or hospitalizations, and those with allergies or past negative reactions to nicotine replacement, will be screened out of medication eligibility at enrollment to further reduce risks of nicotine administration. All Quit Coaches receive training on smoking cessation pharmacotherapy and assess medical conditions that may preclude or complicate NRT use at registration. In addition, Quit Coaches have access to Optum physicians who can address questions or concerns about pharmacotherapies. Optum will conduct routine monitoring for adverse or unanticipated events according to their standing protocols.

Participants will be alerted to possible withdrawal effects at enrollment, will be offered over-the-counter medication to manage these symptoms (if medically eligible), and will be advised that these symptoms are typically mild and temporary.

Optum, the WTQL vendor, employs physicians to review medication protocols and has a rigorous adverse event monitoring protocol. All medications will be dispensed in ways that are consistent with the protocol and packaging instructions, with clear instructions. No more than a 4-week supply will be provided. Participants experiencing side effects will be advised to seek local

medical care as needed, with the understanding that the costs of the medical care will be the responsibility of the participant (or the participant's insurer), as discussed in the consent process.

The risk of aversive withdrawal symptoms will be addressed in two ways. First, standard WTQL practice addresses the nicotine withdrawal syndrome in an individually tailored manner. This will not change in the current study. Second, we will provide nicotine replacement to all participants, in accordance with best practice and current practices at the WTQL. All participants will be advised that they can call the WTQL for additional coaching calls, as needed, so even those in the single-scheduled-counseling-call-condition will have access to ongoing support regarding the management of nicotine withdrawal. Everyone medically eligible for NRT will receive at least nicotine patches (and half will receive lozenges in addition to patches) to address withdrawal during the first 2-4 weeks of the smoking cessation effort.

**Explain why the risks to the subjects are reasonable in relation to the anticipated benefits.**

This study carries minimal risk. None of the interventions to be deployed poses significant risk above and beyond standard WTQL treatment and every participant will receive at least one form of evidence-based smoking cessation treatment. No information about illegal behavior will be entered in databases. The risk of someone's identity becoming known to unauthorized persons is low. This risk is outweighed by the benefits of quitting smoking for any individual, and the benefit to society of having fewer people use tobacco products. This research has the potential to benefit low-income smokers in the future by helping to identify optimal combinations of remotely delivered interventions for population-wide dissemination. The proposed project will accelerate refinement of treatments with broad reach and low barriers to access using an efficient factorial research design. The risks associated with the use of over-the-counter nicotine patches and nicotine lozenges are minor relative to the risks of continued smoking, particularly with the medication eligibility screening used by the WTQL. If successful, this treatment approach could be used more broadly to reduce the considerable financial and personal costs associated with smoking-related disease. Therefore, the potential gain in knowledge regarding treatments and mechanisms of change associated with the proposed study outweigh the risks of participation.

**Describe the provisions in place to identify and address unanticipated problems or complications.**

The Principal Investigators (PIs) will be responsible for routinely monitoring study progress. Optum, the WTQL vendor, has an adverse event monitoring protocol and team in place and will alert the study PIs to adverse events among study participants. Any data safety concerns will be reported to the study PIs immediately and addressed. We will report any unanticipated problems to the IRB according to posted guidelines. A full data safety and monitoring plan is included at the end of this protocol.

**Describe the precautions that will be used to ensure subject *privacy* is protected**

Collection of sensitive information about subjects will be limited to the amount necessary to achieve the aims of the research. Participants will not be asked to disclose any information about illegal behavior.

**Describe the measures that will be implemented by your research team to safeguard the identifiable subject information from unauthorized use or disclosure for both paper and electronic forms of information. Include how and where data will be stored.**

Participant study data will be collected by the WTQL through a Computer Assisted Telephonic Interview (CATI) and will be stored on secure, password protected servers. Data will be

accessible only to assigned study staff for their study function; computer workstations will be password-protected, thus secured from unauthorized use. WTQL will transmit study data—enrollment information, randomization data, all assessment data, service utilization data, and identifying information to CTRI via a secure FTP site. On a monthly basis, identifiable research data including contact data needed to conduct follow-up interviews at UW-CTRI, will be transmitted through a secure FTP site by the WTQL to UW-CTRI.

Data received from participants in SmokefreeTXT are overseen by the site sponsor (National Cancer Institute). SmokefreeTXT data regarding completion of the program will be transmitted to the WTQL so staff there may process the \$30 incentive for completing the program for those in the active incentive conditions. At the end of the study, more complete data on participant engagement in SmokefreeTXT will be transmitted to UW-CTRI for analyses via a secure FTP site.

Required patient identifying data will be stored in a separate file linked to all study data via a study identifier after it is received from WTQL and SmokefreeTXT. Confidentiality of participant data and information will be accomplished by using participant numbers as unique identifiers, allowing us to keep participant data separate from identifying information. Once transferred to UW-CTRI, data generated through study participation and data obtained on medical and psychiatric history from participants will be stored in secure databases under protections and procedures consistent with the guidelines and regulations of the UW School of Medicine and Public Health (UW-SMPH). Outside access is available only via an encrypted connection to the Department of Medicine Citrix server located at the UW Clinical Science Center in Madison. The servers at the UW-CTRI Madison office are physically secured in a locked room. Data backups are created nightly and stored in a locked safe. Significant safeguards have been implemented to protect data including virus and adware protection, firewall, access controls and encryption when appropriate such as wireless and remote access. All UW-CTRI staff members have completed HIPAA and human subjects training and are aware of the sensitivity of study-related data. The UW SMPH has developed school-wide data security policies and procedures. UW-CTRI data security policies and procedures conform to those of the SMPH. UW-CTRI will use an enterprise-level database that supports audit trails such as access, change logging, and more sophisticated access control for managing and tracking user access privileges. No publications or presentations resulting from this research program will contain any identifying information about individual participants. Following cleaning and verification of data at the conclusion of the study, all research data will be placed in a de-identified data set at UW-CTRI.

## **Data Safety and Monitoring Plan**

The Data Safety and Monitoring Plan (DSMP) for this research comprises not only the research conducted directly by the University of Wisconsin Center for Tobacco Research and Intervention (UW-CTRI) researchers, but also research conducted by other investigators collaborating with UW-CTRI-funded projects. All investigators must agree to comply with the procedures outlined in this DSMP. This DSMP does not reduce any investigator's obligation to comply with the requirements of the Institutional Review Board (IRB) at his/her home institution or the IRB of any collaborating organizations.

*Monitoring the progress of trials and the safety of participants.* The Principal Investigators (PIs) are responsible for routine monitoring of study progress. This includes scheduled meetings with study staff at least monthly; review of weekly reports from the Wisconsin Tobacco Quitline (WTQL) vendor, Optum, whose personnel will recruit, screen, enroll, counsel, and compensate participants for treatment engagement; and review of monthly reports of use of SmokefreeTXT. Weekly reviews of WTQL reports and follow-up discussions as needed to address any concerns with Optum are vital as the study procedures, database queries, and reports are being developed,

launched, and refined in the first year of the project. Following roll-out, monthly review meetings will continue to monitor progress and to consider up- or down-regulating the rate of recruitment from month to month. Data reviewed at these meetings will include the number and type of participants enrolled, the number and reasons for exclusions from enrollment, the number of counseling sessions completed, the number of SmokefreeTXT enrollees who opt-out, and the timeliness and accuracy of incentive payments to participants. Adverse or unanticipated events reported at WTQL counseling calls will be addressed using standard WTQL protocols to address medication side effects, withdrawal, or other concerns. The DSMC will review reports on adverse events reported to the WTQL. Adverse or unanticipated events (e.g., failure to receive an earned incentive) reported by participants directly to UW-CTRI through proactive participant calls (participants will receive this contact information at enrollment) will be reported to Optum to record and attempt to resolve the event, and will be reported to the IRB, FDA, or NCI, as appropriate based on the severity and protocol relevance of the event.

To facilitate participant safety, study participants must meet study inclusion and exclusion criteria. Once enrolled, WTQL protocols will assess NRT eligibility and the presence of AEs and SAEs during treatment. Should either excessive risk to study participants and/or convincing evidence of lack of measurable benefit to study participants be determined, the study will be stopped and all participants notified in a manner appropriate to the nature of the risk and/or lack of benefit. When taking that step, the investigators will consult with the IRB and NCI.

Plans for assuring compliance with requirements regarding the reporting of adverse events. This DSMP requires that investigators notify NIH and the University of Wisconsin IRB in a timely manner (consistent with IRB and NIH policies) of the occurrence of any SAE or any AE which is severe, unexpected, and possibly related to study medication or protocol. Because this study involves pharmaceutical agents, if an unexpected SAE might be related to study drug use, both the Food and Drug Administration (FDA) and the manufacturer will also be notified within 5 days of investigators becoming aware of the event. Examples of unexpected SAEs would be untoward medical or intervention occurrences that result in death, are life-threatening, require hospitalization or prolonging of existing hospitalization, create persistent or significant disability/incapacity, or involve congenital abnormality/birth defects. Unanticipated AEs include less serious problems that merit reporting to the DSMC because they are severe, unexpected, and possibly related to study participation. Any SAE will be queried and reported even if it appears that the serious adverse event is unrelated to study participation. Because the interventions will be delivered by our WTQL partner, Optum, staff there will be responsible for assessing and managing any adverse events related to study medication in accordance with their existing protocols for monitoring NRT medication side effects or unanticipated health events during counseling calls. The study team will review Optum reports of unanticipated health events no less than bi-weekly, and Optum will notify the PIs of any severe, unanticipated, and possibly study-related adverse events in a timely manner so that NIH, FDA, and the IRB may be notified, as needed.

Adverse event assessment, recording, reporting, and investigation will be accomplished through staff training, structured/standardized assessments of untoward occurrences/events, and regular monitoring by Optum staff and the study team. The PIs have ultimate responsibility for ensuring that SAEs are detected and reported in a timely manner. Additionally, the IRB will receive an annual report of all SAEs and AEs meeting the criteria listed above.

Plans for assuring that any action resulting in a temporary or permanent suspension of an NIH-funded clinical trial is reported to the NIH grant program director responsible for the grant. The NIH grant program director will be notified within 5 days if the PIs deem it necessary to suspend

the clinical trial. In the case of a temporary suspension, the PIs will develop a plan for continuation of the study and discuss this plan with the NIH grant program director in a reasonable time frame.

Plans for assuring data accuracy and confidentiality and protocol compliance. The UW-CTRI PIs will develop protocols for assuring UW-CTRI data collection accuracy and protocol compliance (relevant to follow-up assessments). Such protocols will include data verification and protocol compliance checks. The UW-CTRI team will also work with Optum and SmokefreeTXT to ensure that their protocols have similar quality assurance standards and data security checks. The researchers at UW-CTRI will abide by the uploaded Data Use Agreement terms for use of SmokefreeTXT use data. The Data Manager and PIs will also be responsible for ensuring that the data for the project are securely transferred from Optum and SmokefreeTXT and stored at UW-CTRI, and that storage is in compliance with University and federal regulations and that no unauthorized persons have access (electronic or physical) to any participant-identifiable data. HIPAA regulations and guidelines are currently implemented at UW-CTRI and Optum, and all study staff must complete approved human subjects and HIPAA training programs.

Inter-site data transfers are accomplished via secure file transfer protocols (SFTP) using an internet server maintained by the UW School of Medicine and Public Health (UWSMPH) Department of Medicine. To protect the privacy of database records and the integrity of the network, this server is firewall-protected and is stored in a locked server room with a numeric keypad to restrict entry. The server is continuously scanned for the presence of viruses. A complete virus scan of all workstations also takes place once a week. Server system log files are scanned for unusual activity, which is immediately investigated. Network and Server Administration staff members apply critical and non-critical patches as needed. In addition, the UW-CTRI and the UWSMPH Department of Medicine also have multiple mechanisms for preserving confidentiality of research participants and providing data security in the transfer of data from participant machines to the SFTP server. The Department of Medicine web servers use Secure Socket Layer (SSL or https) technology to encrypt data exchanged between the client and the server. In addition, all online and offline components of the data systems described in the proposal will be accessible only through a login and password unique to each user. The security access levels for these login accounts are tiered and the features and privileges given to each staff member will be determined by the PIs and IT Manager. To further protect confidentiality, only the UW-CTRI IT Manager will be permitted to transmit data to the SFTP server. Finally, the Department of Medicine employs extensive data backup and server redundancy procedures and performs full backups to tape weekly of all servers, along with incremental and daily backups.

Data and Safety Monitoring Committee. In addition to the protections outlined in the DSMP (above), all research activities conforming to the NIH definition of a clinical trial will also have an independent Data Safety and Monitoring Committee (DSMC). This application includes a Phase IV clinical trial using FDA-approved medications. The DSMP specifies overall monitoring that will be conducted by Optum, as the intervention deliverer, and by the PIs, including timely reporting of AEs and SAEs. Every six months, the DSMC will convene to review the overall safety data, as well as data on safety summarized by treatment condition. As per NIH guidelines, the objective of these reviews will be to determine whether continued conduct of the trial poses any undue risk for participants.

The existing UW-CTRI DSMC is chaired by [name], leader of the Cancer Control Program of the UW Comprehensive Cancer Center. [name] is an experienced physician and clinical trial researcher with no involvement in any of this project's research activities. [name] is joined on the DSMC by [name] and [name]. [name] is Associate Professor of Medicine and Medical Director of the HIV/AIDS Comprehensive Care Program at UW Hospital and Clinics who has previously collaborated on a clinical trial of smoking cessation with

UW-CTRI. [name] is an otolaryngologist who has served on independent DSMBCs for Phase II and III trials involving a nicotine vaccine. Neither has direct involvement with any of the proposed research. The PIs will report to the DSMC; the three DSMC members will be unblinded as to treatment conditions and will make the final determinations as to study continuation.

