Cost data will come from: research participants who will report on their out-of-pocket costs of tobacco and treatment and health care utilization at enrollment and follow-up; Optum who will report on intervention delivery, supply, and support costs; SmokefreeTXT who will report minute/data use costs associated with cumulative message volume and the estimated cost per user for the program; and from public data sources (on the costs and savings associated with cessation and continued smoking).

The population will be the eligible, consented, enrolled subjects who were randomized to treatment. Participants who were randomized but did not complete the study will be included. Analyses will occur in the full intent-to-treat sample whenever possible, using model estimation that permits missing data. Utilization rates have important implications for intervention costs, so both low and high utilizers of intervention components will contribute important data to these analyses.

Cost and efficacy data (abstinence outcomes assessed in Aim 1) will be used to estimate the costs per verified quit by treatment condition, in accordance with recommendations for cost-effectiveness analyses. These data will also be used to estimate costs per quality-adjusted-life-year (QALY) saved, based on prior estimates of QALY associated with smoking status. As recommended by Feirman et al. sensitivity analyses will be conducted, using alternative QALY measures to assess robustness of estimates. We can

use data from the project's factorial design to generate smoothed estimates of the costs per quit and costs per QALY for different combinations, using multivariate regression analysis. We will also estimate potential savings related to reduced smoking levels, as a function of previous smoking frequency and the estimated effects of the interventions on quitting or self-reported post-intervention smoking frequency. This approach could use information from the factorial design to create smoothed estimates of personal savings.

***Data Sources and Collection:*** Participants will self-report health care utilization and spending on tobacco and cessation treatments; Optum will report on WTQL intervention costs; and SmokefreeTXT will report on the volume of text message exchanges and total costs per user. UW-CTRI will collate data from these sources for analyses.

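### The safety plan must report any SAE, but names no step for recording or forwarding events learned at the 12- and 26-week interviews

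*Combined protocol and SAP*

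**What the plan says.** **Intake.** The Data Safety and Monitoring Plan (DSMP), under monitoring of progress and safety, describes two specific routes.

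- The vendor's calls: "Adverse or unanticipated events reported at WTQL counseling calls will be addressed using standard WTQL protocols". The DSMP adds that "WTQL protocols will assess NRT eligibility and the presence of AEs and SAEs during treatment".
- Events "reported by participants directly to UW-CTRI through proactive participant calls (participants will receive this contact information at enrollment"). These go to Optum to record and, where appropriate, to the IRB, FDA or NCI. The remark about contact information shows that the participant starts these calls.

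**Duty.** The DSMP's text on adverse event reporting is broad: "Any SAE will be queried and reported even if it appears that the serious adverse event is unrelated to study participation". Its SAE examples include death and events that "are life-threatening, require hospitalization or prolonging of existing hospitalization".

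**Onward reporting.** "Optum will notify the PIs of any severe, unanticipated, and possibly study-related adverse events in a timely manner". On the committee: "The DSMC will review reports on adverse events reported to the WTQL". The DSMC section adds a six-monthly review of safety, overall and by treatment condition.

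**Follow-up interviews.** UW-CTRI conducts them, in windows of 11-18 and 25-38 weeks after the quit day (section G and Assessment Plan). The content listed in the Assessment Plan and the Schedule of Study Activities covers tobacco use, treatment use, costs, satisfaction and mediators. It includes no adverse event item and no hand-off. The Analysis Plan for Aim 2, however, says participants report "health care utilization at enrollment and follow-up".

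**The concern.** The reporting duty covers any SAE from any source, while the described intake covers contacts with the vendor and calls that participants choose to make. The two interviews are the study's own scheduled contacts with every participant, and they fall outside both routes. A hospital stay mentioned there could remain in the Aim 2 cost data without being flagged as an SAE.

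A second consequence is statistical. If routine capture runs mainly through counseling calls, the chance of recording an event depends on how many calls a participant was randomized to. A higher event count in the four-call conditions could then reflect more asking rather than more harm, and a low count in the one-call conditions could give false reassurance. The DSMC is asked to judge undue risk from summaries of this kind.

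**Working it through.** The plan states no SAE rate and no detection figure, so there is none to reproduce. The main check is a side-by-side reading.

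| Question | Specific text | General text |
|---|---|---|
| Which events must be reported? | Any SAE, related or not (DSMP) | Same |
| When are events assessed? | During treatment, on counseling calls (DSMP) | Standardized assessment and monitoring by Optum and the study team; no time point or instrument named (DSMP) |
| What is passed from UW-CTRI to Optum? | Events from participant-initiated calls (DSMP) | Not stated |
| What reaches the PIs? | From Optum: severe, unanticipated, possibly related events (DSMP) | Safety concerns at once (section H); Optum reports of unanticipated health events reviewed at least every two weeks (DSMP) |
| What reaches the DSMC? | Events reported to the WTQL (DSMP) | Overall safety data; the PIs report to the DSMC (DSMC section) |

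In the last four rows the specific wording is narrower than the duty in the first. The general text closes the gap as an obligation, but does not say who does what after an interview.

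**Planned capture by randomized factor.** Inputs: 1 or 4 scheduled calls (Goals/Aims); N of 1,408 to 1,600 (section A). Planned calls per half-sample = (N/2) × calls.

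- N = 1,408: 704 × 1 = 704 versus 704 × 4 = 2,816.
- N = 1,600: 800 × 1 = 800 versus 800 × 4 = 3,200.

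This is a fourfold difference in scheduled opportunities. Incentive conditions also pay $30 per counseling call, which is meant to raise the number completed.

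The design limits where this bites. In the 16-cell table each NRT level has four one-call cells and four four-call cells, so the mean is (4 × 1 + 4 × 4)/8 = 2.5 scheduled calls at both levels. On scheduled calls alone, the pooled NRT contrast is balanced. The contrast by counseling level, and comparisons of single cells with different call numbers, are not.

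**Follow-up time after scheduled contact (illustration).** The documents do not date the four calls, so I assume that scheduled contact ends at week 4, 6 or 12. Share of 26 weeks remaining = 1 − t/26:

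- t = 4: 85%
- t = 6: 77%
- t = 12: 54%

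**Events in that period (illustration).** I assume 2%, 5% or 10% SAEs per person-year; no rate is given in the documents. Expected SAEs in 26 weeks = N × rate × 26/52; those after week 6 = that figure × 20/26.

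| N | Rate | In 26 weeks | After week 6 |
|---|---|---|---|
| 1,408 | 2% | 14.1 | 10.8 |
| 1,408 | 5% | 35.2 | 27.1 |
| 1,408 | 10% | 70.4 | 54.2 |
| 1,600 | 2% | 16.0 | 12.3 |
| 1,600 | 5% | 40.0 | 30.8 |
| 1,600 | 10% | 80.0 | 61.5 |

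Across all the assumptions, the count after scheduled contact runs from 7.6 (N = 1,408, 2%, week 12) to 67.7 (N = 1,600, 10%, week 4). These are events that occur after the last scheduled call. They are not events shown to be missed, since participants may still call in.

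**The case against.** The strongest reply is that the duty is already written and is not limited by source. Section H sends safety concerns to the PIs immediately. The DSMP makes the PIs ultimately responsible for detecting and reporting SAEs and promises standardized assessments with monitoring by the study team. The DSMC section has the PIs report to a committee that reviews overall safety data. An interviewer who heard of a hospital admission would be expected to pass it on.

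This stands, and it rules out two inferences a reader might draw: that counseling calls and participant-initiated calls are the sole sources, and that an event heard at interview has no path to the PIs or the DSMC. The general clauses contradict both. It would also be wrong to say that capture on counseling calls relies on participants volunteering events, because the DSMP says WTQL protocols assess for them.

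Other limits also stand:

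- The follow-up questionnaire (Attachment G) and Optum's adverse event protocols are separate documents. An adverse event item or a forwarding instruction in them cannot be excluded.
- Only the Aim 2 text places health care use at follow-up. What the interview asks about hospital stays is not visible.
- A reader might suppose that deaths would surface through household members or contact persons. Those contacts are collected to help the WTQL, and section G does not list them among the contact data sent to UW-CTRI, so that pathway is conjecture.
- The NRT supply is over the counter and lasts at most four weeks, so events first heard of at weeks 25-38 may say little about medication risk.

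None of this supplies the missing step. The general clauses name no time point, instrument or hand-off for the interviews, and interviewers blind to condition and without other participant data need an explicit instruction.

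**Conclusion.** The point holds as a mismatch between duty and procedure. The obligation to detect, query and report any SAE is present, but the specific intake, hand-off and DSMC wording is narrower and leaves out the 12- and 26-week interviews. Optum's criterion for notifying the PIs is also narrower than the any-SAE rule in the same part of the DSMP; the two should be reconciled.

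The firm quantity is the fourfold difference in scheduled calls, which leaves by-condition summaries open to unequal ascertainment. The direction and size of any distortion depend on completed calls and on Optum's protocols, neither of which is known. The balanced design protects the pooled NRT contrast as far as scheduled calls go. The event counts are illustrations under assumed rates, and the conclusion does not rest on them. The primary abstinence analysis is not affected. The change is worth making because it is cheap and carries out a duty the plan already accepts.

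**What to change.** In the DSMP:

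1. Replace the words that confine UW-CTRI reports to participant-initiated calls with: *on any contact, including the 12- and 26-week interviews and third-party reports*.
2. State that deaths and hospitalizations learned this way are logged as SAEs, queried, and forwarded to the PIs, Optum and the DSMC.
3. Extend the sentence on DSMC review to events known to UW-CTRI, and align Optum's notification criterion with the any-SAE rule.
4. Before each six-monthly DSMC review and at close-out, reconcile follow-up health-care-use answers with the SAE log.
5. In the Assessment Plan, state whether health care use and adverse events are asked about at each interview, so that it agrees with the Aim 2 text.

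Interviewers forward the event only and stay blind. Optum, which performs the randomization, can attach the condition for the DSMC.

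The cost is brief protocol wording, a short log, and a small recurring reconciliation: two a year over 3-4 years of recruitment is 6 to 8, plus those during remaining follow-up and at close-out. The downside is more unrelated hospitalizations to process, which the any-SAE rule already accepts. Since both interviews are scheduled alike in every condition, recording events there would also reduce the dependence of capture on the number of calls.
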